16.7. Causality Assessment

An adverse event is not automatically related to the study device or procedure simply because the subject is wearing the device and participating in the study. The event should be reviewed to determine if the device or study procedure could have possibly caused the event and therefore is related to the study device or procedure.

Causality assessment is the determination of the relationship between an adverse event and the device being studied. A causal relationship is present if a determination is made that there is a reasonable possibility that the adverse event may have been caused by the device or a study procedure. It is expected

that the investigational center will review all elements surrounding the adverse event to properly assess the causality of the event to the study device or to a study procedure.

This review would include the subjects description of the event, study device uploads and medical records (if applicable) from the treating facility. These records will be made available to sponsor.

The following definitions should be considered when determining the relationship of the event to the device or study procedure:

Causal Relationship – clearly related to the device or procedure

Probable – likely related to the device or procedure

Possible – may be related to the device or procedure

Unlikely – doubtful that event is related to the device or procedure

Not Related – clearly not related to the device or procedure

16.8. Anticipated or Unanticipated

If the adverse event is determined to be related to the study device or study procedure the Investigator must then assess the event to determine if it is anticipated or unanticipated.

- **Anticipated:** the event is identified in the CIP; labeling; report of priors or user guide.
- **Unanticipated:** the event has not been previously identified in the CIP; labeling; report of priors, Investigator brochure, or user guide.

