Note 2: The term "life-threatening" in the definition of "serious" refers to an event in which the patient was at risk of death at the time of the event; it does not refer to an event which hypothetically might have caused death if it were more severe. (ICH Topic E 2 A Clinical Safety Data Management: Definitions & Standards for Expedited Reporting. EMEA 2006)

Serious Adverse Device Effect (SADE) (ISO 14155-2011)

Adverse device effect that has resulted in any of the consequences characteristic of a serious adverse event

Unanticipated Adverse Device Effect (UADE) (21 CFR 812.3(s)) equivalent to USADE (ISO14155-2011 3.42)

Any serious adverse effect on health or safety or any life-threatening problem or death caused by, or associated with, a device, if that effect, problem, or death was not previously identified in nature, severity, or degree of incidence in the investigational plan or application (including a supplementary plan or application), or any other unanticipated serious problem associated with a device that relates to the rights, safety, or welfare of subjects.

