1. UADE
2. DKA
3. Severe hypoglycemia events that result in subject requiring paramedic assistance, an ER visit or subjects who experience seizure, coma or death:
 - Site will notify the sponsor on the same day after receiving knowledge of the event. If the event becomes known to the site after hours, then it should be reported to the sponsor the next day.
 - Sponsor will notify FDA and the country-specific regulatory agency in the EMEA region within 24 hours of knowledge of event and provide updates to those agencies as information becomes available.
 - Enrollment will be stopped after the above events have been reported
 - DSMB is to review the event within 48 hours from the time that sponsor is notified. If possible, the investigator should be available to answer questions by DSMB.
 - DSMB will provide recommendation to sponsor on the following:
 - If enrollment may resume
 - If the entire study has to be stopped, including subjects who have already received study devices.

20. Ethical and Regulatory Considerations

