
Risks associated with hypoglycemia include:
 
 • Seizure • Coma • Altered mental status • Loss of consciousness • Cardiovascular event • Death • Risk of rebound hyperglycemia with ketosis 	
Prevention and mitigation risks of infusion sets include:
 
 • Investigational center staff and subjects and their parent(s)/guardian(s)/companion(s) will be instructed to follow the provided user guides for insulin pump management. • Parent(s)/guardian(s)/companion(s)s will be present at night with subjects and will be trained on study device and diabetes management principles and told to call with problems. • Subjects and their parent(s)/guardian(s)/companion(s) will be trained prior to study on device use device and diabetes management principles.

Potential Risk with Sensor
	
Mitigation

Potential risks with Sensor include:
 
 • Skin irritation or reaction to adhesives • Bruising • Discomfort • Redness • Bleeding • Pain • Rash • Infection • Irritation from tapes used with glucose-sensing products • Raised bump • Appearance of a small "freckle-like" dot where needle was inserted • Allergic reaction • Syncopal episode secondary to needle insertion • Soreness or tenderness • Swelling at insertion site • Sensor fracture, breakage or damage • Minimal blood splatter associated with sensor needle removal • Residual redness associated with adhesive and or tapes • Scarring • Incorrect sensor glucose reading results in incorrect diabetes management • Subject over-treating secondary to alarms which can result in hyperglycemia or hypoglycemia 	
Prevention and mitigation risks of Sensor include:
 
 • Investigational center staff and subjects and their parent(s)/guardian(s)/companion(s) will be instructed to follow the provided user guides for insertions and care of sensors. If a sensor site becomes infected or inflamed, the sensor should be removed and another placed in a new location. • Subjects and their parent(s)/guardian(s)/companion(s) are instructed to use fingerstick glucose reading for diabetes management and diabetes management decisions and told to call with problems.

Potential Risk with Serter
	
Mitigation

Potential risks with Serter use include:
	
Prevention and mitigation risks of Serter include:

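### Sections 16.6 and 16.8 test differently whether a serious device effect was foreseen, so the UADE trigger for the study-wide hold can be missed or delayed

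*Protocol*

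**What the plan says.** Section 16.6 takes its definitions from ISO 14155:2011 and 21 CFR 812. It makes a serious device effect a UADE if it "was not previously identified in nature, severity, or degree of incidence in the investigational plan or application".

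Section 16.8 then gives the investigator a step to carry out: "If the adverse event is determined to be related to the study device or study procedure the Investigator must then assess the event" as anticipated or unanticipated. It is anticipated if "the event is identified in the CIP; labeling; report of priors or user guide". It is unanticipated if "the event has not been previously identified in the CIP; labeling; report of priors, Investigator brochure, or user guide".

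UADE is the first of three study-wide triggers in Section 19.2, repeated in the synopsis. The second is DKA. The third is "Severe hypoglycemia events that result in subject requiring paramedic assistance, an ER visit or subjects who experience seizure, coma or death". The consequences include notice to regulators within 24 hours, DSMB review within 48 hours of the sponsor being told, and this: "Enrollment will be stopped after the above events have been reported". UADE also drives the 10-working-day report to the IRB/EC (16.4), is one item of the Suspend before Low success criteria (11.4.7), and is a summarized safety result (22.3, 24.2).

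**The concern.** The definition asks three things about a serious effect: its kind, how bad it was, and how often it occurs. The only classification step in the protocol that addresses anticipation asks one thing, namely whether the event is named somewhere. A brief entry in a risk table is enough to make an event anticipated under 16.8, at any severity or frequency.

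This matters because serious device effects other than DKA and the listed severe hypoglycemia reach the enrollment hold only through the UADE label. The study's stated purpose is to show safety, its subjects are as young as 2 years, and the sponsor classes it as significant risk (20.1). The definition that opens the hold should have one reading.

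**Working it through.** No figure is involved, so the check sets the texts side by side and follows one event through them.

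| | 16.6 (UADE) | 16.8 (anticipated or unanticipated) |
|---|---|---|
| Applies to | Serious effects, life-threatening problems and deaths associated with a device, plus a residual clause for other serious problems | Every device- or procedure-related AE, serious or not |
| What must have been identified | Nature, severity and degree of incidence | The event |
| Where | The plan or application | Four sources under Anticipated; the same four plus the Investigator brochure under Unanticipated |

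1. **Severity.** The sensor row of Table 2 (20.4.1) lists "Allergic reaction" and infection, with no grade. A life-threatening form of either can be a UADE under 16.6, because that severity was not identified. Under 16.8 it is anticipated, because the term is there.

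2. **Incidence.** Table 2 gives no rates. Serious site infections occurring unexpectedly often can be UADEs under 16.6; 16.8 never asks about frequency. Cellulitis needing hospitalization is already given as an example in 16.2, so it illustrates incidence better than severity.

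3. **Sources.** An event named only in the brochure fails the Anticipated bullet, which omits the brochure, and also fails the Unanticipated bullet, which requires that the brochure not name it. It has no class. The study-binder list in 23.6 pairs the brochure with the report of priors; if the two are one document here, this is only a wording slip.

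4. **Effect on 19.2.** Suppose the site uses 16.8 and labels the event in step 1 anticipated. It is neither DKA nor listed hypoglycemia, so no trigger fires. Under 16.3 it still goes to the sponsor within 24 hours as an SAE or SADE. Under Section 17 the DSMB adjudicates it, but the assured timing is the routine meeting, at least every 6 weeks. That is up to 6 × 7 = 42 days, against 48 / 24 = 2 days for a UADE: as much as 40 days longer if no extra meeting is called, with enrollment open meanwhile.

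5. **Effect on 11.4.7.** The criteria require no UADE, no device-related SAE and no DKA. A serious device effect fails the second item whatever its anticipated label. Only the residual clause of the UADE definition could fall outside that item.

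6. **Effect on reporting.** Sections 22.3 and 24.2 also list SAEs and SADEs. The event is reported there and missing only from the UADE line.

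**The case against.** The best reply is that the protocol has only one UADE test. Section 16.6 states it in full, 16.8 never mentions UADE, and 19.2 uses the defined term. On this reading 16.8 is a general label for all related AEs, and a miss requires a site to put that label in place of an explicit definition. In addition, the sponsor sees every SAE and SADE within 24 hours and decides on regulatory reporting (16.1, 16.3). The DSMB may disagree with the investigator's classification, and it reviews device-related events, including whether they were unanticipated (17).

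Much of this stands. It makes a miss possible rather than certain, and reduces much of the harm to delay. It does not remove the conflict: no section says that 16.6 prevails, 16.8 is the step the investigator must perform, and Section 17 does not say which test the DSMB applies.

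A reader might also infer that a relabelled event would let Suspend before Low pass its safety criteria. The separate bar on device-related SAEs rules that out, apart from the residual clause. Another tempting reading is that every grave term in Table 2 becomes anticipated in any setting. The table does not support this. Heart failure appears under saline infusion, and shock under the risks of hyperglycemia. Coma and death appear as consequences of glycemic events, and DKA and hypoglycemic coma or death have their own triggers. For infusion sets only localized infection is named. The unqualified sensor entries are the sound examples.

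**Conclusion.** The conflict is real and should be corrected. Its reach is limited to serious device effects other than DKA and the severe hypoglycemia listed in 19.2, and it takes effect only if 16.8 is used to decide UADE status, which the protocol does not exclude. In that case one misclassified event is enough to leave the hold, the 24-hour regulator notice and the 48-hour review unstarted, and to leave the UADE count one short. The DSMB would still see the event, but with assured timing of weeks rather than two days.

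A reader might conclude that the UADE count must be zero for such events, or that they vanish from the safety results. The documents support neither: a site or the DSMB may apply 16.6, and the SAE and SADE summaries still contain the event. No hypothesis test, power calculation or efficacy endpoint is affected.

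**What to change.** Reconcile 16.8 with the protocol's own definition in 16.6:

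- State in 16.8 that, for serious device effects, anticipated or unanticipated status follows 16.6 (nature, severity, degree of incidence).
- State in 19.2 that its UADE trigger uses the 16.6 definition.
- Keep the simple named-event label for non-serious related AEs. Applying the three-part test to every related AE would make listed minor effects such as bruising or redness unanticipated, because Table 2 states no rates.
- Use one identical source list in both bullets of 16.8, and say how it relates to the plan or application named in 16.6.

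The cost is a few sentences, and possibly a few more events sent for expedited DSMB review. Design, sample size and study procedures do not change.

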16.9. Severity of Event (Intensity)

A clinical determination of the intensity of the event will be made. The following guidelines should be used:

- **Mild:** transient, needing no special treatment, and/or does not interfere with the subject's daily activity.
- **Moderate:** low level of inconvenience or concern to the subject and may interfere with daily activities, but is usually improved by simple therapeutic remedy.
- **Severe*:** interrupts a subject's daily activity and typically requires intervening treatment.

*Please Note: In the classification of adverse events, the term “**severe**” is not the same as “**serious**.” The term “**severe**” relates to an indication of the intensity of a specific event (as in mild, moderate, or severe chest pain). The term “**serious**” relates to a participant/event outcome or action criteria, usually associated with events that pose a threat to a participant's life or functioning.

17. Data Safety Monitoring Board

A DSMB consisting of external physicians with an expertise in Endocrinology and the management of insulin requiring diabetes including CGM, along with an external statistician will be convened to review study progress, endpoints and safety.

The DSMB will perform a number of functions:

1. Adjudication of the following events:

- Serious Adverse Event
- Serious Adverse Device Effect
- Unanticipated Adverse Device Effect
- Severe Hypoglycemia

- Diabetic Ketoacidosis

The DSMB will assess these events to determine agreement or disagreement with the Investigator classification of the event. The Sponsor will notify the Investigator of any disagreement in assessment of an event by the DSMB. The DSMB will meet a minimum of every 6 weeks to adjudicate these events unless there are no events to adjudicate.

2. DSMB will track and trend the overall Safety of the study.

Incidence for the following will be reviewed by the DSMB:

- Incidence of all SAEs.
- Incidence of severe hypoglycemia
- Incidence of DKA
- Incidence of device related adverse events.

Applicable information for device related adverse events may include:

- Whether or not the event was unanticipated
- Review of sensor data from CareLink report (when applicable)
- Review of pump data from CareLink report (when applicable)
- Misuse of the device by the user

3. The DSMB will meet sooner if there is a DKA event, a UADE or a severe hypoglycemia event as outlined in the stopping rules for the entire study:

- DSMB is to review the event within 48 hours from the time that the sponsor is notified. If possible, the investigator should be available to answer questions by DSMB.
- DSMB will recommend a decision to the sponsor on the following:
 - Whether or not enrollment will continue to be on hold
 - Whether or not the entire study will need to be stopped including for those subjects who have received study devices already.

4. The DSMB will provide a recommendation to the sponsor on whether or not pediatric subjects 2-4 years of age will be permitted to enroll into the study. The recommendation is based on a review of data from 10 subjects 5-6 years of age after they have completed the first month of the study period.

General guidance for DSMB's recommendations to sponsor should be based on the following:

Review of events may require the following information. Final disposition of an event may be delayed based on obtaining this information:

- Monitoring by sponsor at site
- Device return and failure analysis
- Carelink upload and review of Carelink reports
- Subject clarification to site regarding details about the event
- Source documents that support event: Paramedic records; ER records; Lab records; Hospital admission and discharge summary

The following factors should be carefully considered in the DSMB's recommendation to sponsor:

1. Was the severe hypoglycemia or DKA related to the HCL algorithm, SmartGuard with predictive threshold suspend or was it related to a known insulin pump risk? For example, a question that may

be considered in DKA would be whether the event was related to an infusion set issue or caused by the HCL algorithm.

2. Another important consideration would be if the severe hypoglycemia or DKA event was related to a device malfunction versus patient non-compliance. For example, if a software anomaly leading to an under-delivery of insulin is discovered versus the subject repeatedly ignoring alarms prompting the subject to take action.
3. Severe hypoglycemia or DKA caused directly by an infusion set issue when the study pump is functioning as intended would likely result in acceptance to proceed with the study versus severe hypoglycemia or DKA that are directly caused by the HCL algorithm or a device malfunction might stop study enrollment or entire study altogether.
4. It should be noted that the final determination of causality related to the HCL System or SmartGuard with predictive threshold suspend that is made by the DSMB may include additional factors which the members consider to be clinically relevant and important.
5. The DSMB may take into account the thresholds listed below for the number of subjects experiencing hypoglycemia requiring assistance from another person, hypoglycemia resulting in seizure or loss of consciousness or DKA to identify when the number of subjects experiencing these events exceeds the number that would be anticipated for the study population over the duration of this study. These thresholds should be interpreted with caution due to potential differences in study populations and study design.

Adverse Event	Reference Rate (<26 years old)	Reference Rate (≥26 years old)
Hypoglycemia requiring assistance from another person to administer oral carbohydrates, glucagon or other resuscitative actions	≤4 subjects experiencing one or more events during study ¹	≤7 subjects experiencing one or more events during study ¹
Low blood glucose resulting in seizure or loss of consciousness	≤2 subjects experiencing one or more events during study ²	≤3 subjects experiencing one or more events during study ³
DKA	≤ 3 subjects experiencing one or more events during study ²	≤ 2 subjects experiencing one or more events during study ³

The event thresholds for hypoglycemia requiring assistance from another person is derived from the JDRF study of continuous glucose monitoring and intensive treatment of type 1 diabetes. The event thresholds for low blood glucose resulting in seizure or loss of consciousness is derived from the rate reported in T1D Exchange Clinic Registry. The rates reported in these previous studies are adjusted for the 3 month study period with 130 expected subjects to determine the maximum number of subjects expect to experience one or more of these events during the study.

1. Juvenile Diabetes Research Foundation Continuous Glucose Monitoring Study Group, Tamborlane WV, Beck RW, Bode BW, Buckingham B, Chase HP, Clemons R, Fiallo-Scharer R, Fox LA, Gilliam LK, Hirsch IB, Huang ES, Kollman C, Kowalski AJ, Laffel L, Lawrence JM, Lee J, Mauras N, O'Grady M, Ruedy KJ, Tansey M, Tsalikian E, Weinzimer S, Wilson DM, Wolpert H, Wysocki T, Xing D. Continuous glucose monitoring and intensive treatment of type 1 diabetes. N Engl J Med. 2008 Oct 2;359(14):1464-76


18. Withdrawal Procedures

Subjects may choose to withdraw from the study at any time by notifying investigational center staff of their intent.

Individual subjects will not be replaced

If a subject chooses to end his or her study participation or if a subject is removed from the study at the Investigator's discretion, the reason for termination must be documented both in source documents and on the appropriate eCRF. All study devices and supplies must be returned and the return documented both in source documents and on the appropriate eCRF.

Subjects may also be withdrawn from the study at the discretion of the Investigator. A subject will be withdrawn from the study if:

- In the opinion of the Investigator, the subject's health or safety would be compromised by continuing in the study
- In the opinion of the Investigator, it is in the subject's best interest to discontinue participation in the study
- During the course of the study, subject begins participation in another investigational study (drug or device).
 - Please note should the subject elect to remain in the continued access program: Subjects will be permitted to participate in other studies during the continued access period of the study with Sponsor permission, provided that the studies do not include the use of drugs or devices, i.e. devices not used in this study.
- During the course of the study, subject begins abusing illicit drugs or marijuana.
- During the course of the study subject begins abusing prescription drugs.
- During the course of the study subject begins abusing alcohol.
- During the course of the study subject begins using pramlintide (Symlin) DPP-4 inhibitor, liraglutide (Victoza or other GLP-1 agonists), metformin, canagliflozin (Invokana or other SGLT2 inhibitors).
- During the course of the study, subject receives red blood cell transfusion or erythropoietin.
- During the course of the study, subject persistently wears sensor for longer than the labeled 6 days.
- During the course of the study, the subject demonstrates that he/she is not able to comprehend instructions for study procedures, as evaluated by the appropriate research staff.
- During the course of the study, subject takes any oral, injectable, or IV glucocorticoids.
- During the study, (female) subject becomes pregnant.
- During the study, the subject experiences a severe hypoglycemic episode
- During the study, the subject experiences DKA
- During the study subject has a cardiovascular event or any vascular event such as stroke
- Subject proceeds into Auto Mode during the **run-in period**.

Documentation of the reason(s) leading to subject withdrawal will be kept in the subject's source file.

For EMEA only: If patient withdrawal is due to problems related to the investigational device safety or performance, the investigator shall ask for the subject's permission to follow his/her status/condition outside the clinical investigation.

19. Stopping Rules

If it is decided to prematurely terminate the patients participation in the study or prematurely terminate the entire study the subjects will be followed-up in accordance with standard practice.

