2.1.8. Charger (MMT-7715)

The Charger (MMT-7715) is used to recharge the GST3C Transmitter as needed. A fully charged battery provides up to 7 days of GST3C Transmitter use. The system includes a battery charger that will recharge the device according to the user guide. Not commercially available in Israel.

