2.1.9. Charger (MMT-7715) – US approved

The Transmitter Charger (MMT-7715) is used to recharge the Guardian Link (3) Transmitter as needed. A fully charged battery provides up to 7 days of Guardian Link (3) Transmitter use. The system includes a battery charger that will recharge the device according to the user guide. Not commercially available in Israel.

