- Subjects and parent(s)/guardian(s) will be requested to call study staff if they have glucose levels above 300 mg/dL with elevated ketone levels accompanied by nausea, vomiting, or inability to drink fluid.
- Ketone testing requirements

⁵ **Study Meter:** If the Study Meter reading falls outside the stated control solution (control solution for Study Meter is investigational must only be used with the Bayer meter) range, then testing with new test strip(s) will be repeated until the reading falls within the appropriate control solution range (see Study Meter user guide materials). If a Study Meter's reading remains outside the control solution range after 3 attempts, a new Study Meter will be provided.

⁶ **Ketone Meter:** If the Ketone Meter reading falls outside the stated control solution (control solution for Ketone Meter is specific to device) range, then testing with new test strip(s) will be repeated until the reading falls within the appropriate control solution range (see Ketone Meter user guide materials). If a Ketone Meter's reading remains outside the control solution range after 3 attempts, a new Ketone Meter will be provided.

⁷ One handbook will be provided per subject and parent(s)/guardian(s)/companion(s); the handbook will be reviewed for the following:

- Train subjects and their parent(s)/guardian(s)/companion(s) on the devices as well as diabetes management principles such as the treatment of hyperglycemia or hypoglycemia and having access to oral glucose in case of hypoglycemia.

- Instruct subjects and their parent(s)/guardian(s)/companion(s) to change infusion sets when infusion set catheter occlusion is suspected. Insulin via syringe may need to be given, especially if ketones are present.
- Review general pump management with parent(s)/guardian(s)/companion(s). It is understood that in order to be eligible for the study, patients must be pump users. This part of training will be a refresher.

⁸ Sensor Details:

- The sensor must be calibrated to ensure correct operation.
- The Investigator may allow a subject to leave the center prior to sensor initialization.
- If subjects encounter any calibration problems with the sensor, the sensor may be replaced to ensure correct operation.
- Subjects, with the assistance of parents/guardians, should replace the sensor after 7 days of use (upon receiving a “Sensor expired” alert) or as events dictate throughout the course of the study.

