Train subjects and their parent(s)/guardian(s)/companion(s) on CGM, the proper use of the Sensor and the Study Pump. The investigator or qualified research staff will provide recommendations whether or not the sensor glucose low and high alerts should be turned on or off and, if turned on, at which threshold they should be set.			X							
Instruct subjects on sensor calibration requirements ³			X							
Train subjects on Run-in Period requirements ⁴			X							
Instruct subjects and their parent(s)/guardian(s)/companion(s) that sensors must be worn continuously throughout the study and that successful sensor wear with pump CGM will be a condition for continued study participation			X	X	X	X	X	X		
Instruct subjects and their parent(s)/guardian(s)/companion(s) to check blood glucose at least 4-6 times per day for diabetes self-management (SMBG), using the supplied Study Meter according to the user guide. Subject compliance with SMBG will be encouraged and will be used at the end of the run-in period to determine whether or not subjects are suitable to move into the study period		X	X	X	X	X	X	X		
Train subjects and their parent(s)/guardian(s)/companion(s) on the Auto Mode feature of the study pump					X					
Train subjects and their parent(s)/guardian(s)/companion(s) on specific considerations regarding Auto Mode ⁵					X					

CEP302DOC: Pivotal Pediatric Hybrid Closed Loop Study

CEP302DOC

Revision J

Page 52 of 102

Study Activities (Training and Instruction)	Screening Visit 1	Visit 2	Visit 3 (Start Run-in)	Visit 4 (End Run-in)	Visit 5 (Start Study Period)	Study Period Interim Office Visit	Study Period Phone/Office Visits	Study Period Hotel/House or Clinic	End of Study Period Visit	Continuation Period Visits
Instruct subjects and their parent(s)/guardian(s)/companion(s) that they should not assume that Auto Mode is able to prevent all hypoglycemia or all hyperglycemia including diabetic ketoacidosis					X					
Instruct/Remind subjects that the use of Acetaminophen is not allowed during the study 
 If acetaminophen is taken, subjects will be instructed to use additional BG meter readings (they are not to calibrate with those readings) to verify their glucose levels. Subjects will be instructed to exit AutoMode 					X	X	X	X	X	

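### Section 18 withdraws a child for repeatedly wearing sensors past 6 days, but the visit-schedule instructions tell families to change them at 7 days

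*Protocol*

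**What the plan says.** Section 18 (Withdrawal Procedures) opens its list of criteria with "A subject will be withdrawn from the study if". One entry is that the "subject persistently wears sensor for longer than the labeled 6 days". The sentence just before the list reads "Subjects may also be withdrawn from the study at the discretion of the Investigator", and earlier in the same section the protocol states "Individual subjects will not be replaced".

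Section 11.3 gives a different wear limit. Footnote 8 (Sensor Details), attached to the sensor-insertion row of the site-activities table, says that subjects, helped by their parents or guardians, "should replace the sensor after 7 days of use". It ties the change to the pump's sensor-expired alert and allows for replacement at other times as circumstances require. The training table in the same section has families told that "sensors must be worn continuously throughout the study".

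**The concern.** The 6 days is a decision threshold: crossing it persistently is a listed reason to take a child out of the study. The 7 days is the routine that families are trained to follow. If both stand, the trained routine satisfies the withdrawal criterion.

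Either number could be the wrong one, and each case has a cost:

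- **If the label is 7 days**, Section 18 penalises correct use. Sites would apply it unevenly, and a literal reader could withdraw a compliant subject.
- **If the label is 6 days**, footnote 8 directs children to wear sensors past labeled life. In Auto Mode the pump calculates insulin doses from those sensor values (Sections 2.1.1 and 2.1.2).

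The rule is also monitored. The sponsor's surveillance reports (Section 11.3, sponsor-activities table, footnotes 1 and 2) cover sensor wear and sensor re-starts. Their stated purpose is to find non-compliant subjects who may need to be withdrawn, and they refer staff to the withdrawal procedures, where the 6-day figure stands.

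**Working it through.** The protocol derives no figure on this point, so the check is a comparison of every statement that bears on how long a sensor is worn.

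| Place in protocol | Figure | What it governs |
|---|---|---|
| Section 18, withdrawal list | 6 days, described as labeled | Life of one sensor; persistent excess leads to withdrawal |
| Section 11.3, footnote 8 | 7 days, at the expiry alert | Life of one sensor; instruction to families |
| Sections 2.1.3 and 2.1.4, sensor descriptions | None | No wear life stated for Enlite 3 or Guardian Sensor (3) |
| Section 2.1.8 | "A fully charged battery provides up to 7 days of GST3C Transmitter use" | Transmitter battery, not sensor |
| Section 2.1.9 | "A fully charged battery provides up to 7 days of Guardian Link (3) Transmitter use" | Transmitter battery, not sensor |
| Section 11.1, run-in success criteria | 2,880 data points, equal to 10 days | Total wear over the run-in, not one sensor |
| Section 11.3, surveillance footnotes | No day limit | Monitoring of wear and re-starts |

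Only the first two rows set a limit for a single sensor, and they differ. No text gives one limit to the investigational sensor and the other to the approved one, or separates them by study period.

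**Size of the gap.** 7 − 6 = 1 day per sensor worn to the alert, and 1/6 = 16.7%, about 17% beyond the withdrawal limit.

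**Whether the qualifier on persistence resolves it.** Wear is meant to be continuous, and Section 8.2 gives a study period of 96 to 110 days. Changing at 7 days uses 96/7 = 13.7 to 110/7 = 15.7 sensors, or about 14 to 16. A child who waits for the alert each time exceeds 6 days on essentially every one of them, which is persistent by any ordinary reading. The qualifier excuses an isolated late change but not the instructed routine.

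**The case against.** The strongest counter-argument is that the Section 18 criterion is anchored to the label, and the label is outside the protocol. Section 2 refers to the device manuals for instructions for use, and the row carrying footnote 8 itself refers to the labeling. On that view the target is a subject who keeps a sensor going past expiry, and the surveillance item on sensor re-starts fits that reading. No site is told to flag a child who changes at the alert. The sentence on investigator discretion and the undefined word for persistence leave further room for judgment. A family could also satisfy both texts by changing at day 6, since continuous wear means no gaps between sensors and does not require each one to run to its alert. Finally, the plan allows for attrition: up to 200 enrolled to reach 120 completers (Section 5), and at least 95 enrolled where 80 are needed (Section 24.3.3).

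Much of this limits the harm. The sensible reading is probably the common one, the attrition allowance means that a few lost subjects would not undermine power, and no endpoint or analysis is shown to be affected. None of it removes the contradiction. Section 18 states a number and calls it the label. The discretion sentence does not alter that number, and the list itself is worded as mandatory. Changing at day 6 avoids the conflict only by departing from the routine in footnote 8. That the protocol does not show the labeled life is a reason to look it up, since one of the two texts must then be corrected or the difference explained.

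**Conclusion.** The concern holds. Two operative passages set different wear limits for the same sensor, 1 day apart, and a subject who follows the family instruction literally meets a withdrawal criterion. The probable effect is modest: inconsistent compliance judgments between sites and an occasional unnecessary withdrawal. If 6 days is the true label, there is instead a standing instruction to wear sensors beyond it.

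The conclusion rests on the current protocol text alone. It assumes that families follow the alert as instructed. It does not assume which figure is correct, and it claims no number of withdrawals and no change in sample size or power. It should be fixed because the figure decides whether a child stays in the study, and the correction is very cheap.

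**What to change.** Look up the labeled wear life and the expiry-alert setting of the MMT-7020 sensor in both configurations, Enlite 3 and Guardian Sensor (3). Then use one number throughout:

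- **If the label is 7 days**, change the Section 18 criterion to 7 days.
- **If the label is 6 days**, change footnote 8 to 6 days. Because the footnote links replacement to an alert after 7 days, also check when that alert fires, and tell families to change the sensor before it if necessary.
- **If the two configurations differ**, state which limit applies to which, in both places.

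In the expected case the cost is a label check and a one-digit edit, with no new procedures, data or analyses.
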